2.2. Study Objectives

2.2.1. Primary

- To evaluate the safety and tolerability of single and multiple ascending intravenous (IV) and subcutaneous (SC) doses of PF-06835375 in participants with SLE and RA.

2.2.2. Secondary

1. To evaluate the effect of PF-06835375 on depletion of circulating CXCR5 positive B cells and cTfh cells in participants with SLE and RA.
2. To characterize pharmacokinetics (PK) profile of PF-06835375 in participants with SLE and RA.
3. To evaluate immunogenicity of PF-06835375 in participants with SLE and RA.

CCI

CCI

3. INTERIM ANALYSES, FINAL ANALYSES AND UNBLINDING

This is a sponsor open study, with the investigator and subject blinded to study treatment. To minimize the potential for bias, treatment randomization information will be kept confidential by Pfizer personnel and will not be released to the investigator/study staff until the conclusion of the study. Final analysis will follow the official database release.

Specific Pfizer personnel (clinician, statisticians, and clinical pharmacologists) will be un-blinded to subject treatment assignments in order to permit real-time interpretation of the pharmacokinetic, flow cytometry and safety data, and to provide information necessary to potentially alter the dose escalation sequence.

4. HYPOTHESES AND DECISION RULES

4.1. Statistical Hypotheses

No statistical hypotheses will be tested in this study.

4.2. Statistical Decision Rules

No statistical decision rules will be used for this study.

5. ANALYSIS SETS

5.1. Full Analysis Set

The full analysis set is comprised of all randomized participants.

5.2. Pharmacokinetic Analysis Sets

5.2.1. Concentration Analysis Set

The PK concentration population is defined as all enrolled participants treated who have at least 1 concentration.

5.2.2. Parameter Analysis Set

The PK parameter analysis population is defined as all enrolled participants treated who have at least 1 of the PK parameters of interest.

5.3. Pharmacodynamic Analysis Set

The pharmacodynamic analysis population is defined as all enrolled participants who receive at least 1 dose of study medication and have at least 1 pharmacodynamic measurement.

5.4. Safety Analysis Set

All participants who receive at least 1 dose of study medication will be included in the safety analyses and listings.

5.5. Other Analysis Sets

None.

5.6. Treatment Misallocations

All analyses will be performed on an “as-treated” basis and will not include data from participants who are randomized but not treated.

If a subject takes a treatment that is not consistent with the treatment they are randomized to, for example takes a treatment out of sequence or takes the same treatment twice, then they will be reported under the treatment that they actually receive for all safety, PK and pharmacodynamic analyses, where applicable.

5.7. Protocol Deviations

Participants who experience events that may affect their PK profile may be excluded from the PK analysis. At the discretion of the pharmacokineticist a concentration value may also be excluded if the deviation in sampling time is of sufficient concern or if the concentration is anomalous for any other reason.

A full list of protocol deviations will be compiled and reviewed to identify major and minor deviations prior to database closure.

5.7.1. Deviations Assessed Prior to Randomization

At screening, the investigator will assess participants against the inclusion and exclusion criteria as set out in Sections 4.1 and 4.2 of the protocol.

5.7.2. Deviations Assessed Post-Randomization

Any significant deviation from the protocol will be reviewed prior to database closure and a decision taken regarding evaluation for each analysis population.

6. ENDPOINTS AND COVARIATES

CCI

6.2. Safety Endpoints

In this section, the safety endpoints that will be measured during the study are detailed. Where applicable, details of the endpoints to be derived and definition of baseline are also provided.

The following data are considered in standard safety summaries (see protocol for collection days and list of parameters):

- *adverse events*,
- *laboratory data*,
- *vital signs data*,
- *ECG results*.

6.2.1. Adverse Events

Any events occurring following start of treatment will be counted as treatment emergent.

Events that occur in a non-treatment period (for example, washout or follow-up) will be counted as treatment emergent and attributed to the previous treatment taken.

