2. STUDY OBJECTIVES AND ENDPOINTS

Primary Objective:	Primary Endpoints:

 To evaluate the safety and tolerability of single and multiple ascending intravenous (IV) and subcutaneous (SC) doses of PF-06835375 in subjects with SLE and RA. 	
 Incidence of dose limiting or treatment related adverse events (AEs). Incidence, severity and causal relationship of treatment emergent AEs (TEAEs) and withdrawals due to treatment emergent adverse events. Incidence of abnormal chemistry, hematology, and urinalysis laboratory findings through the end of study. Abnormal and clinically relevant changes in vital signs and electrocardiogram (ECG) parameters. Incidence of infections.
Secondary Objectives:	Secondary Endpoints:

 To evaluate the effect of PF-06835375 on depletion of circulating CXCR5 positive B cells and cTfh cells in subjects with SLE and RA. To characterize pharmacokinetics (PK) profile of PF-06835375 in subjects with SLE and RA. 	
 Change from baseline in the number of circulating CXCR5 positive B cells and cTfh cells on Day 29 single dose of PF-06835375 and at Week 8 following multiple doses of PF-06835375. Serum PF-06835375 PK parameters after single and multiple doses: 
 Single Ascending Dose Phase: C_{max}, T_{max}, AUC_{inf}, AUC_{last}. Multiple Ascending Dose Phase: 
 First Dose: C_{max}, T_{max}, AUC_{tau}. Multiple Dose: C_{max}, T_{max}, AUC_{last}, AUC_{tau}, C_{min} and observed accumulation ratio (R_{ac}), peak-to-trough ratio (PTR).

 To evaluate immunogenicity of PF-06835375 in subjects with SLE and RA. 	
 Incidence of development of anti-drug antibodies (ADAs)/neutralizing antibodies (Nabs).
CCI	

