3. STUDY DESIGN

3.1. Study Overview

This is a Phase 1, randomized, multi-center, double-blind, sponsor open, placebo-controlled, single and multiple dose-escalation study to evaluate the safety, tolerability, pharmacokinetics, and pharmacodynamics of PF-06835375 in subjects with seropositive SLE or RA. Both IV and SC routes of administration will be tested.

This study will include two parts: Part A, consisting of approximately eight single ascending dose (SAD) cohorts, and Part B, consisting of approximately 6 multiple ascending dose (MAD) cohorts. Fewer cohorts may be included in each part at Sponsor's discretion. Cohorts in Part A will be initiated sequentially. Subjects in Part B will receive two doses of investigational product (first dose on Day 1 and second dose on Day 29), and will be enrolled concurrently with Part A following the completion of the initial cohorts in Part A (See [Section 3.3](#)). Subjects who are randomized in Part A will not be eligible to participate in Part B of this study.

[figure not shown]
This study will enroll up to a total of approximately 112 subjects at approximately 10 sites.

The study includes a Screening visit to assess eligibility and subsequent visits for a minimum of 16 weeks. Subjects who meet the end of study criteria (See [Section 3.5](#)) will have one follow-up phone call visit which will represent the end of study visit. Subjects, who do not meet the criteria to leave the study at Week 16, will continue with clinic visits every four weeks until Week 52 and then every 12 weeks until they meet these criteria. Overall, subjects are expected to stay in the study approximately 6-12 months (including screening). Subjects who withdraw from the study may be replaced at the discretion of the sponsor. A replacement subject will receive the same treatment as the withdrawn subject.

Both SLE and RA subjects will be enrolled into this study. Minimum disease activity (ie, [CCI](#) [REDACTED] or DAS28 cutoffs) is not required for entry as inclusion criteria. All subjects in both Part A and B will be followed for a minimum of 16 weeks prior to being able to qualify for study completion based on the cellular recovery (See [Section 3.5](#)).

It is at the sponsor's discretion to dose escalate (See [Section 3.4.1](#)), to repeat the same dose, or to test a lower dose based on emerging data.

[CCI](#)

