3.5. Criteria for End of Study

All subjects will be followed through the Week 16 visit. In order for the Week 16 visit to be the subject's last clinic study visit, B cell counts meet at least one of these criteria:

- B cell count is \geq 50% of baseline value AND is stable or increasing between Week 12 and Week 16 measurements, OR
- B cell count is \geq lower limits of normal (defined as 80 cells/ μ l¹⁹) at Week 16.

If at least one of the above criteria are not met at Week 16, subjects will continue in the study and will be followed until B cell count meets at least one of these criteria:

- B cell count is \geq 50% of baseline value AND is stable or increasing between the two measurements at least two weeks apart, OR
- B cell count is \geq lower limits of normal (defined as 80 cells/ μ l¹⁹), OR
- B cell count reaches a new stable (or increasing) detectable level AND subject is clinically stable for minimum of two consecutive visits, each at least two weeks apart, based on the assessment by both the sponsor AND the investigator. The earliest B cell count that can be considered for this criterion is from the Week 20 visit. As a result, subjects will not be discharged prior to availability of Week 24 lab results for B cells under this criterion.

B-cell counts obtained from CLIA certified central lab will be used for this determination.

Baseline value is defined as the average of Screening and Day 1 pre-dose values. In cases where only one value (ie, screening or Day 1 pre-dose) is available, this one value will be used as the baseline. Stable is defined as ± 5 cell/ μ l. Values obtained by the central lab will be used.

B cell counts data will be available only after subject completes the clinic visit due to the required shipment of samples to central lab and their processing time. Once subject meets the criteria for the end of study described above, a phone visit will take place within approximately 1-2 weeks, prior to the next scheduled in clinic visit. This phone visit will be considered the end of study visit/last visit.

Subjects may be asked to return for additional follow up visits beyond the anticipated end of study visit for safety reasons as determined by the Investigator in consultation with the sponsor medical monitor.

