- f. Current or past history of either 1) active tuberculosis (TB) infection or 2) latent TB that was inadequately treated or where adequate treatment cannot be documented.
- g. Clinically significantly abnormal chest X-ray per investigator opinion or evidence of active TB on chest X-ray. Subjects who had chest X-ray performed within 3 months prior to the Screening visit do not have to have chest X-ray performed, provided documentation is available.

13. Known hypersensitivity, intolerance or allergic reaction to the IP or placebo or any of its excipients, or history of severe hypersensitivity to monoclonal antibodies.
14. Known hypersensitivity or allergic reaction to pre- or post-infusion medications (corticosteroids, acetaminophen and antihistamines).
15. Known hypersensitivity or allergic reaction to Td or Trumenba vaccination.
16. Received any live virus or live-attenuated vaccines within 4 weeks prior to Screening, or expected during the study period (from Screening to subject's last visit).
17. Received plasmapheresis within 12 weeks prior to Screening or expected during the study period (from Screening to subject's last visit).
18. History of or planned organ transplant for the duration of the study (from Screening to subject's last visit).
19. Major surgery requiring use of general anesthesia within 6 weeks prior to Screening or planned or expected major surgery during the study period (from Screening to subject's last visit).
20. History of any malignancy within past 5 years prior to Screening (except adequately treated and removed basal and squamous cell carcinomas of the skin, and in situ cervical cancer intraepithelial neoplasia of the uterine cervix).
21. Subject abused drugs or consumed an excessive amount of alcohol in the past 12 months, based on the opinion of the investigator.
22. Presence of any of the following laboratory abnormalities at Screening:
 - B-cell count at Screening below the lower limit of normal (LLN), defined as 80 cells/ μ l (obtained from CLIA certified central lab).

- Total serum IgG <5 mg/dl (or 5 g/l).
- Hemoglobin <10 g/dL (100 g/L).
- White blood cell count <2.5 x 10⁹ /L (<2,500/mm³).
- Platelet count <75 x 10⁹/L per central laboratory results (75,000/mm³).
- Neutrophil count <1.5 x 10⁹/L (<1,500/mm³).
- Aspartate aminotransferase (AST) **or** alanine aminotransferase (ALT) level $\geq 2.0 \times$ upper limit of normal (ULN).

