8.1.4. Time Period for Collecting AE/SAE Information

The time period for actively eliciting and collecting AEs and SAEs (“active collection period”) for each subject begins from the time the subject provides informed consent, which is obtained before the subject’s participation in the study (ie, before undergoing any study-related procedure and/or receiving investigational product), through and including and including a minimum of 90 calendar days after the last administration of the investigational product. For subjects who are in the study beyond 90 calendar days after the last administration of the investigational product (expected for most subjects), the end of study visit will be used as a minimum cut-off.

For subjects who are screen failures, the active collection period ends when screen failure status is determined.

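### Follow-up after Week 16 depends on B-cell counts, so whole-follow-up percentages for adverse events, infections and abnormal labs are not like-for-like between dose groups and placebo

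*SAP*

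**What the plan says.** **Length of follow-up.** Protocol 3.5: "All subjects will be followed through the Week 16 visit". A subject can finish there if the B-cell count is at least 50% of baseline and stable or rising since Week 12, or is at least 80 cells/µL. Otherwise follow-up continues until one of those conditions is met or a third applies: "B cell count reaches a new stable (or increasing) detectable level AND subject is clinically stable for minimum of two consecutive visits". The earliest count usable for the third is Week 20, so it cannot release anyone before Week 24 results are in. Visits are every 4 weeks to Week 52 and every 12 weeks after that (Protocol 3.1). Protocol 4.2 excludes a "B-cell count at Screening below the lower limit of normal (LLN), defined as 80 cells" per µL. Protocol 3.1 says that "subjects are expected to stay in the study approximately 6-12 months (including screening").

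**What is counted.** SAP 6.2.1: "Any events occurring following start of treatment will be counted as treatment emergent". It extends this to non-treatment periods: "for example, washout or follow-up) will be counted as treatment emergent". For subjects still in the study more than 90 days after the last dose, Protocol 8.1.4 says "the end of study visit will be used as a minimum cut-off". The primary laboratory endpoint in Protocol 2 covers "urinalysis laboratory findings through the end of study". SAP 8.3.4 and 8.3.5 refer adverse-event and laboratory reporting to the sponsor's reporting standards and name no window. SAP 8.3.6 counts every post-dose time point in the vital-sign categories.

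**The concern.** B-cell depletion is the intended effect of the drug, and the B-cell count decides how long a subject is observed after Week 16. Treatment and dose therefore influence time at risk. Suppose two groups have the same underlying event rate and one is watched longer. The longer-watched group will show a higher percentage with at least one event, as long as the rate after Week 16 is not zero.

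Incidence of adverse events, infections and abnormal laboratory findings are primary endpoints. The by-treatment columns sit beside placebo, and a reader will compare them. The readable SAP plans no follow-up time per group next to those percentages, so the reader cannot tell how much of a gap reflects longer observation.

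**Working it through.** **1. The plan's own figures.** Table 2 of the protocol sums to 4×4 + 4×8 + 5×8 + 24 = 112, matching the stated enrolment. The cohorts that SAP 2.1 lists as used (A1–A6, B1–B5) are expected to hold 54 active and 18 placebo subjects. Protocol 9.1 says the sample size has no statistical basis, so no power or alpha figure is at stake.

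**2. Direction of the effect.** Entry needs at least 80 cells/µL and a count of at least 80 at Week 16 permits exit, so an undepleted subject would usually leave then. Depletion is planned: Protocol 1.3 predicts about 50% at the lowest dose, and Protocol 3.3 expects Part B to start once Part A counts fall to about 10 cells/µL. Depleted groups should therefore stay longer, probably with little difference in the lowest cohorts.

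**3. Lengths of stay used.**
- 17.5 weeks: Week 16 plus 1.5 weeks, the middle of the 1–2 weeks to the phone visit.
- 25.5 weeks: Week 24 plus 1.5 weeks, about the earliest exit under the third criterion.
- 33 weeks: middle of the stated stay. 9 months less 45 days of screening is (273.9 − 45)/7 = 32.7 weeks. The ends of the range, 6 and 12 months, give 19.7 and 45.8 weeks.

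**4. Adverse events and infections.** The rate r is assumed and equal in both groups. After 17.5 weeks the hazard is either unchanged (f = 1) or cut to a quarter (f = 0.25):

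H(w) = r×17.5/52.18 + f×r×(w − 17.5)/52.18; proportion with an event = 1 − exp(−H).

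At r = 1 per subject-year:

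| Stay | H (f = 0.25 / 1) | Proportion | Of 6 active |
|---|---|---|---|
| 17.5 weeks | 0.335 | 28% | 1.7 |
| 25.5 weeks | 0.374 / 0.489 | 31% / 39% | 1.9 / 2.3 |
| 33 weeks | 0.410 / 0.632 | 34% / 47% | 2.0 / 2.8 |

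Over r = 0.3 to 2 and both hazard shapes, the ratio to 17.5 weeks is 1.08–1.42 at 25.5 weeks and 1.14–1.81 at 33 weeks.

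**5. Abnormal labs, Part A schedule only.** There are 10 scheduled post-dose draws to Week 16 (Day 1 post-dose, Days 2, 4, 8, 15 and 29, Weeks 6, 8, 12 and 16) and 14 to Week 32. With an assumed probability p per draw and independent draws, the proportion is 1 − (1 − p)^n. At p = 3% this gives 26% against 35%. For p from 1% to 5% the ratio is 1.28–1.37. A beta-binomial with within-subject correlation 0.3 gives ratios of 1.14–1.15. Part B has a different schedule and was not counted.

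**6. Vital-sign categories, Part A.** There are about 24 post-dose readings to Week 16, about 15 of them on Day 1, and about 31 to Week 44. At 2% per reading, 1 − 0.98^24 = 38% and 1 − 0.98^31 = 47%, a ratio of 1.21; with correlation 0.3 it is 1.08. The effect is small even over this long follow-up.

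**7. Is there already a common window?** The windows in the readable SAP serve other outputs: ECG maxima over 0–12 hours, and the cytokine-release screen on Days 1–3 or 1–4. The analysis in Protocol 9 that is triggered when all subjects reach Week 16 or discontinue sets when data are analysed. It does not cut each subject's data at Week 16.

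**The case against.** Counting every post-dose event is the cautious choice in a first-in-human study of a B-cell depleter, and it agrees with the protocol's collection period and laboratory endpoint. That stands. A reader might infer that the treatment-emergent definition is itself an error, but the documents do not support that.

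The SAP tests no hypotheses and plans no formal safety analysis. Explicit dose-minus-placebo summaries are planned only for vital signs and ECG by time point, and these are unaffected. For adverse events and labs, the comparison is one the reader makes from descriptive columns. This lowers the severity without removing the problem, because these are primary endpoints in a placebo-controlled study.

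The sponsor's reporting standards were not supplied and parts of the SAP are redacted, so a window may exist there. This stands too: the gap can be claimed only for the readable text.

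Depleted subjects need not recover fully to leave. The third exit criterion needs only a stable detectable count in a clinically stable subject, with stable meaning ±5 cells/µL. Escalation also required most active subjects in a cohort to have detectable counts at two visits from Week 12 (Protocol 3.4.1). Neither rule caps the stay, but together they make about 25.5 weeks plausible for many. The gap there is 0.2–0.6 of a subject in six.

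Disposition tables and listings give partial protection, and follow-up time can be derived from collected data.

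**Conclusion.** The point holds as a gap in presentation. In the readable plan, whole-follow-up percentages for adverse events, infections and abnormal labs mix drug effect with time observed, and no common-window table or follow-up time per group accompanies them. They remain a valid description of risk over the time observed. They are not a like-for-like comparison with placebo.

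The direction follows from the design, given that placebo subjects mostly leave soon after Week 16, which is inferred from the shared 80 cells/µL threshold. The size is illustrative: event rates, hazard shapes and per-draw probabilities are all assumed, and each scenario gives a whole group a single length of stay although exits are individual.

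A reader might take the top of the stated stay, about 46 weeks, and infer that the apparent incidence doubles (59% against 28% at a constant 1 per subject-year). The documents do not support that as the expected case. The 6–12 months describes subjects overall, not depleted groups; exit is possible from Week 24; and SAP 2.1 reports that A7, A8 and X6 were not used and that the doses in A6, B4 and B5 were reduced.

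Severity is minor to moderate, because the study is descriptive and cohorts have 3–6 active subjects.

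**What to change.** Keep the through-end-of-study summaries and add to the SAP:

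1. By-treatment tables of adverse events, infections and abnormal labs restricted to Day 1 to Week 16, the period planned for every subject.
2. Median follow-up and total person-time per group beside the whole-follow-up tables.

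If the sponsor standards already set a window, state it in SAP 6.2.1.

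Exposure-adjusted rates are optional. If shown, split them at Week 16. An unsplit rate assumes a constant hazard and can make longer-followed groups look safer: with f = 0.25 and identical groups, it reads 100 per 100 person-years at 17.5 weeks but 0.410/(33/52.18) = 65 at 33 weeks. Such rates are also unstable here: 3 active subjects for 17.5 weeks is 1.0 person-year, so one event reads as about 100 per 100 person-years.

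The cost is one extra set of tables from data already collected. Events after Week 16 would appear only in the whole-follow-up tables. Endpoint definitions and existing analyses do not change, so the amendment condition in Protocol 9 for major modifications of the primary endpoints should not apply.

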6.2.2. Laboratory Safety Tests

Safety laboratory tests will be performed as described in the protocol.

To determine if there are any clinically significant laboratory abnormalities, the haematological, clinical chemistry (serum) and urinalysis safety tests will be assessed against the criteria specified in the sponsor reporting standards. The assessment will take into account whether each subject's baseline test result is within or outside the laboratory reference range for the particular laboratory parameter.

Baseline will be the last pre-dose measurement (first treatment for MAD cohorts).

